3.2 Prognosis

The overall median survival for patients with MM is 36 months, with International Staging System stage I, II, and III patients surviving a median of >60, 41, and 23 months respectively.⁴ Several prognostic factors have been identified. An elevated serum level of beta-2 micro-globulin (β2M), a component of the class I HLA molecule, is a powerful prognostic indicator of shortened survival.⁵ Since β2M is excreted by the kidney, renal insufficiency will increase serum levels of β2M. The plasma cell labeling index (PCLI) identifies the percentage of proliferating plasma cells in S phase of the cell cycle and is a powerful independent predictor of progression and survival.⁶ Chromosomal abnormalities, such as translocations t(4;14), del 17p, and t(14;16) confer poor prognosis.^{7,8} Investigators have found that achieving a complete remission early on in the disease may be important in predicting long-term survival.^{9,10} Indeed, Kyle *et. al* suggested that an objective response to standard therapy is by far the most important feature of long-term survivors.¹¹ Major controlled trials have confirmed this seminal observation even in the context of high-dose chemotherapy.¹² Based on those observations, the goal of achieving an early complete remission should allow patients to sustain long-term survival and perhaps lead to a cure.

Myeloma is still an incurable disease and obtaining an initial long disease-free interval prior to relapse is important to prolong patient survival and improve quality of life. At the present time, there is still a need for new and effective induction therapies for the newly diagnosed multiple myeloma patients to achieve this goal.

3.3 Treatment

Oral dexamethasone and intermittent oral melphalan and prednisone (MP) were widely used standard conventional therapies for MM for many years. Responses, defined as a 50% or greater decrease in paraprotein (aka M-protein or M-spike), were seen in approximately 30-60% of patients. Duration of response to these agents is generally 1.5 to 2 years, with median survival from time of initiation of therapy of approximately 24 to

30 months. Cures are not achieved. Relapses are often marked by the development of drug resistance and by a more aggressive clinical course. Thus, subsequent remissions are more difficult to achieve and are progressively shorter.¹³

Various combination chemotherapy regimens have been developed in an attempt to improve remission rates and duration. These include vincristine, melphalan, cyclophosphamide, carmustine, and prednisone (M2), , vincristine, doxorubicin, and dexamethasone (VAD), vincristine, melphalan, cyclophosphamide, and prednisone alternating with vincristine, carmustine, doxorubicin, and prednisone (VMCP/VBAP), doxorubicin, carmustine, cyclophosphamide, and melphalan (ABCM), amongst other regimens. ^{14 15 16 17} Although these regimens may produce higher response rates and in some cases more rapid tumor mass reduction, a survival advantage has not been demonstrated. Those eligible are often recommended to undergo autologous stem cell transplant, though age and other factors render the majority of patients unable to undergo a successful transplant.

With the advent of novel agents such as thalidomide, lenalidomide and bortezomib there has been a marked improvement in outcomes particularly in younger and fit patients.¹⁸ These agents are discussed more fully below.

3.4 Dexamethasone

Dexamethasone is a synthetic steroid with anti-inflammatory, anti-proliferative, immunomodulatory abilities found to cause apoptosis of myeloma cells.¹⁹ The benefit of VAD (vincristine, doxorubicin, and dexamethasone) over high-dose dexamethasone is marginal (overall response rate 50-55%). A study by the Dutch Hematology-Oncology Group HOVON reports equal overall response rates of 68% when VAD was administered as an IV push and when dexamethasone was given at 40 mg PO QD x 4 only.²⁰ These results suggest that the concurrent administration of VA (vincristine and doxorubicin) does not add major cytoreduction. The results of the 91-155 study at Memorial Sloan-Kettering Cancer Center in which dexamethasone was comparatively intensified show a much higher response rate despite the poor prognostic characteristics of the cohort.⁹ These results indicate that the intensification of dexamethasone is an important factor in determining responses, providing compelling evidence that dexamethasone is by far the most important component in this combination.

3.5 Clarithromycin (Biaxin®)

Biaxin®, or clarithromycin, is a semi-synthetic macrolide antibiotic indicated for the treatment of mild to moderate infections caused by susceptible strains of microorganisms. Pre-clinical studies have shown that Biaxin® has an immunomodulatory effect and may have antineoplastic properties mediated in part by suppression of Interleukin-6 and other cytokines.²¹ Biaxin® has also been shown to modulate the serum half-life of a number of corticosteroids and concurrent biaxin / corticosteroid administration may increase total time of corticosteroid exposure.²² Based upon these properties, the group at Cedars Sinai Comprehensive Cancer Center began a trial using Biaxin® 500mg PO BID for the treatment of newly diagnosed and relapsed/refractory MM patients.²³ Of the 30 patients

treated, 6 patients achieved a complete response, 7 achieved a partial response, 6 patients had stable disease, 4 had a mixed response and 7 patients were too early to evaluate. Follow up studies by other groups in Canada and France have failed to duplicate these promising results.²⁴

3.6 Bixin®, Low-dose Thalidomide and Dexamethasone

Prior experience at the New York Presbyterian Hospital using the combination of Bixin®, low-dose thalidomide and dexamethasone (BLTD) for the treatment of patients with newly diagnosed and relapsed/refractory MM and Waldenstrom's macroglobulinemia have revealed impressive results.²⁵ Of 40 evaluable patients, 37 (93%) achieved a response. Five patients (13%) achieved a complete remission defined by complete disappearance of M-spike and no serologic evidence of disease. Complete (normalization of Ig spike), major (>75% reduction of Ig spike), and partial (>50% reduction of Ig spike) response rates were 40%, 13%, and 27% respectively. A subset of responding patients had been previously resistant to Thalidomide, Dexamethasone, or a combination of the two. These results suggest a synergistic effect amongst the three agents. The response criteria defined above are substantially more stringent than the widely used SWOG criteria. Using the latter, we have obtained a near CR rate (> 75% reduction in Ig spike) of 66%. In order to further our understanding of these findings we have completed a trial randomizing newly diagnosed multiple myeloma patients to receive either low-dose thalidomide or dexamethasone. Patients without a satisfactory response (<50% drop in tumor mass) after 8 weeks of treatment had Bixin® added to their regimen. Results showed that the addition of Bixin® to either regimen seem to dramatically improve both response rate and time to response, even in patients who were previously unresponsive to low-dose thalidomide or dexamethasone. [*unpublished results*]. Using BLTD as a foundation, we sought new approaches to achieve an increase the CR rate, specifically in the form of BiRd therapy (discussed below).

3.7 Lenalidomide (Revlimid®)

Lenalidomide (Revlimid®) is an oral analog of thalidomide with greater potency to activate immunomodulatory effects and inhibit angiogenesis when compared to thalidomide. Both lenalidomide and thalidomide are members of Celgene's proprietary class of compounds called IMiDs® which are characterized by their immunomodulatory and anti-angiogenic activity. In vitro studies comparing the effects of IMiDs® on the production of cytokines and multiple myeloma cell proliferation activity found that lenalidomide was 50 to 2000 fold more potent than thalidomide.²⁶ In addition, lenalidomide's toxicity profile is unique, with fewer non-hematologic side-effects when compared to thalidomide with more predictable and manageable toxicities.

Two phase I studies of heavily pretreated subjects with relapsed or refractory multiple myeloma were conducted to identify the MTD and to evaluate the safety of oral lenalidomide.²⁷ Myelosuppression was found to be the DLT and the MTD was determined to be 25 mg/day. No significant somnolence, constipation, or neuropathy was observed. The first phase I study, 17 (71%) of 24 evaluable patients achieved >25% reduction of the myeloma paraprotein and in the second study, 20% of patients achieved a > 50%

paraprotein reduction (responders received 25-50 mg/day). The results from phase II trials of lenalidomide given at 30 mg per day for 21 days every 28 days suggest that oral lenalidomide is active in advanced multiple myeloma and is well tolerated. Of 46 evaluable subjects with relapsed or refractory MM, 39 (85%) achieved at least stable disease, including 2 subjects with complete resolution of paraprotein.²⁸

Thus, early studies suggest that lenalidomide is active against advanced multiple myeloma and is well tolerated. Currently it is approved in combination with dexamethasone for treatment of relapsed multiple myeloma after a phase III study investigating the effectiveness of lenalidomide with high dose dexamethasone compared to high dose dexamethasone alone in newly diagnosed patients found response for the combination therapy was superior (61% vs. 20%).²⁹ In addition, in vitro analysis determining the effect of low dexamethasone on the anti-myeloma properties of lenalidomide found that dexamethasone works synergistically in antagonizing lenalidomide's immunostimulatory effects and enhancing its antiproliferative properties while independently inhibiting myeloma cell proliferation.

3.8 Rationale for BiRD Combination in Multiple Myeloma

While new anti-myeloma therapies such as bortezomib and immunomodulatory drugs have been developed, multiple myeloma remains an incurable malignancy. Given that obtaining a complete remission with therapy will allow patients with newly diagnosed multiple myeloma to enjoy a higher quality of life and longer duration of freedom from disease symptoms, finding an optimally effective and well-tolerated regimen is imperative.

Based on the immunodulatory effect of biaxin, the unique anti-myeloma activity of lenalidomide, and the synergistic properties of dexamethasone, the combination of BiRd has demonstrated to be highly effective in the treatment of multiple myeloma, and is anticipated to provide superior outcomes when compared to lenalidomide and dexamethasone therapy alone. A phase II study of clarithromycin (500mg twice daily), lenalidomide (25mg daily for 21 days out of a 28 day cycle), and low dose dexamethasone (40mg weekly) called the BiRd regimen was conducted.³⁰ By replacing thalidomide with lenalidomide into our former BLTD treatment platform, we achieved an overall response rate of 90.3%, and a higher CR rate compared with the earlier BLTD data, 30% vs. 13%. Retrospective case matched analysis comparing patients induced with BiRd vs Rd found that the addition of clarithromycin to Rd significantly increased patient's rate of response, with 90.3% vs 79.1% of patients achieving PR or greater, and 45.8% vs 13.9% of patients achieving CR.³¹ While promising, randomized phase III studies are needed to confirm the superiority of BiRd compared with RD in terms of response rates and survival.

This study is intended to investigate the efficacy of combination therapy with an induction phase utilizing a combination clarithromycin (Biaxin[®]), lenalidomide (Revlimid[®]), dexamethasone (Decadron[®]), in multiple myeloma patients who are newly diagnosed and require treatment when compared to patients who receive lenalidomide

and dexamethasone alone. Randomized phase III studies are needed to confirm the superiority of BiRd compared with Rd in terms of response rates and survival. We anticipate the addition of lenalidomide and bixin will lead to a greater CR rate, shorter times to response, and less toxicity. The primary endpoints of this trial include best response rate, toxicities, progression free survival, event free survival, and overall survival.

4.0 INVESTIGATIONAL PLAN

4.1 Study Design

This phase III study, open-label, randomized study investigating lenalidomide and dexamethasone with and without bixin in subjects with newly diagnosed, previously untreated multiple myeloma. Eligible subjects will be randomized in a 1:1 ratio to receive a regimen consisting of either bixin, lenalidomide, and low dose dexamethasone (BiRd arm), or lenalidomide and low dose dexamethasone (Rd arm). Up to 306 patients will be enrolled.

BiRd Arm

Subjects on the BiRd arm will receive bixin, revlimid, and dexamethasone in 28-day cycles. Dosing is as follows:

- Clarithromycin 500mg PO twice daily on days 1-28 for a 28-day cycle. If a dose of clarithromycin is missed, it should be taken as soon as possible on the same day. If it is missed for the entire day, it should not be made up. Vomited doses will not be made up.
- Lenalidomide 25mg PO daily on days 1-21 of a 28-day cycle for patients with a calculated creatinine clearance of ≥ 60 cc/min. Patients with a calculated creatinine clearance of < 60 cc/min will receive 15 mgs PO daily on days 1-21 of a 28 cycle. If a dose of lenalidomide is missed, it should be taken as soon as possible on the same day. If it is missed for the entire day, it should not be made up. Vomited doses will not be made up.
- Dexamethasone 40mg PO will be given on days 1, 8, 15, 22 of a 28-day cycle. Missed or vomited doses will not be made up. If subject cannot tolerate oral dexamethasone, it will be given intravenously.

Rd Arm

Subjects on the Rd arm will receive revlimid, and dexamethasone in 28-day cycles. Dosing is as follows:

- Lenalidomide 25mg PO daily on days 1-21 of a 28-day cycle for patients with a calculated creatinine clearance of ≥ 60 cc/min. Patients with a calculated clearance of < 60 cc/min will receive 15 mgs PO daily on days 1-21 of a 28 cycle. If a dose of lenalidomide is missed, it should be taken as soon as possible on the same day. If it

is missed for the entire day, it should not be made up. Vomited doses will not be made up.

- Dexamethasone 40mg PO will be given on days 1, 8, 15, 22 of a 28-day cycle. Missed or vomited doses will not be made up. If subject cannot tolerate oral dexamethasone, it will be given intravenously.

Correlative studies: Relative dose intensity: Projected total dose per cycle of each component of assigned drug will be divided by the actual dose received and a ratio will be assessed for each cycle delivered.

MRD: Minimal residual disease testing will be performed in subjects who achieve complete response. MRD testing may be performed either by flow cytometry or PCR, whichever is more readily available at the study institution.

Subjects will continue their randomized treatment assignment until disease progression or unacceptable toxicity (whichever occurs first). In case toxicity precludes dosing of one agent (i.e dexamethasone, clarithromycin, lenalidomide), treatment regimen will continue with the remaining agents. Subjects unable to receive ALL the components of the assigned treatment arms will be removed from study after reasonable attempts to dose reduce and manage side effects. Subjects with elevations of AST/ALT greater than three times the upper limit of normal, with concomitant elevation of bilirubin 2 times the upper limit of normal, not attributable to disease, should be discontinued from treatment. Subjects can also be removed from study at investigator's discretion, or if they withdraw consent. At completion or early discontinuation of treatment, subjects will be followed for 30 additional days or up to the initiation of subsequent treatment (whichever occurs first), after which they will be off the active treatment phase of the study. Long term follow up for disease status and survival will proceed until the subject has withdrawn consent, is lost to follow up, or has died.

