10.4 Post Study Follow-up

All attempts will be made to follow patients until progression or death. Subjects who have been discontinued from study will still be followed in a clinic setting to the fullest extent possible on a monthly to bi-monthly basis. Those who choose not to resume regular clinic follow-up will be contacted every 6 months by telephone or electronically

to collect post study information. The post-study collection information will consist of a telephone interview between the clinical investigator and the discontinued patient. The information requested will be current disease status including information about the development of secondary primary malignancies, current treatment use, and physical status of the patient.

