14.2 Sample Size/Accrual Rate

To achieve 90% power to detect a 75% increase in median PFS (44.6 vs. 25.5 months), at the two-sided 0.05 significance level, will require 306 patients total, accrued over approximately 3.0 years (assuming an accrual rate of approximately 9 patients/month), with an additional 12 months of follow-up subsequent to termination of accrual.

When the sample size in each group is 153 patients, with a total number of PFS events required of 133, an exponential maximum likelihood test of equality of survival curves with a 0.05 two-sided significance level will have 90% power to detect the difference between an Arm A (Rd) median PFS of 25.5 months and an Arm B (BiRd) median PFS of 44.6 months (a constant hazard ratio of 1.75); this assumes an accrual period of 3.0 years, a maximum follow-up time of 4.0 years, and no dropouts. The exponential assumption is for planning purposes only, actual analysis will employ nonparametric methods for estimation and testing of survival distributions. Assuming a 10% dropout rate, approximately 337 patients will be accrued to the study.

A futility analysis will be conducted after 50% of the total PFS events required for final analysis has occurred (i.e., 66 of the 133 required PFS events). No accrual suspension is required to conduct the futility analysis. If at this point (i.e., after accumulation of 66 PFS events) the hazard ratio of the control arm over the experimental arm is 1.0 or less, the study will be stopped for futility.

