14.3 Analysis of Progression-Free Survival

Because the analysis of PFS can be difficult, especially in the presence of missing data and lost-to-follow-up, sensitivity analyses can be helpful in determining whether the PFS analysis is robust. As suggested by the alternative PFS definitions recommended in the FDA's Guidance for Industry, "Clinical Trial Endpoints for the Approval of Cancer Drugs and Biologics (May, 2007), the following three types of PFS analyses will be

conducted:

Table A. PFS #1 (includes documented progression only) (Primary PFS Analysis):

Situation	Date of Progression or Censoring	Outcome
No baseline tumor assessments	Randomization	Censored
Progression documented between scheduled visits	Earliest of: 
 • Date of hematological assessment showing progression; or • Date of radiological assessment showing progression; or • Date of urine assessment showing progression 	Progressed
No progression	Date of last hematological, radiological, or urine assessment	Censored
Treatment discontinuation for undocumented progression	Date of last hematological, radiological, or urine assessment	Censored
Treatment discontinuation for toxicity or other reason	Date of last hematological, radiological, or urine assessment	Censored
New anticancer treatment started	Date of last hematological, radiological, or urine assessment	Censored
Death before first PD assessment	Date of death	Progressed
Death between adequate assessment visits	Date of death	Progressed
Death or progression after more than one missed visit	If progression: 
 • Date of hematological assessment showing progression; or • Date of radiological assessment showing progression; or • Date of urine assessment showing progression OR, if not progression: Date of last hematological, radiological, or urine assessment	Censored

Table A represents the primary PFS analysis that only includes well-documented and verifiable progression events. Other data are censored. In Table A, the progression dates are 1) based only on radiological assessments verified by an IRC (clinical progression will not be considered a progression endpoint), 2) assigned to the first time when disease progression is noted, and 3) the date of death when the patient is closely followed. However, deaths occurring after two or missed visits will be censored at the last visit.

Table B. PFS #2 (uniform progression and assessment dates) (PFS Sensitivity Analysis #1):

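### Section 4.1 caps enrolment at 306, while section 14.2 derives 306 with no dropouts and then plans to accrue about 337

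*Combined protocol and SAP*

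**What the plan says.** Section 4.1 (Study Design) gives an upper limit on enrolment: "Up to 306 patients will be enrolled".

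Section 14.2 (Sample Size/Accrual Rate) makes three statements about size.

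- Its opening sentence says that 306 patients in total are required and are accrued over about 3.0 years, "assuming an accrual rate of approximately 9 patients/month), with an additional 12 months of follow-up subsequent to termination of accrual".
- Its second paragraph gives the derivation: "When the sample size in each group is 153 patients, with a total number of PFS events required of 133", with 90% power at the two-sided 0.05 level for medians of 25.5 and 44.6 months. On the conditions it says: "this assumes an accrual period of 3.0 years, a maximum follow-up time of 4.0 years, and no dropouts".
- The same paragraph ends: "Assuming a 10% dropout rate, approximately 337 patients will be accrued to the study".

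No other section reconciles 306 with 337.

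**The concern.** An upper limit of 306 and a plan to accrue about 337 are incompatible. The gap of 31 patients is 10% of 306, too large for "approximately" to absorb. The conflict also runs inside 14.2, where 306 is first the number accrued and later the number before the dropout allowance.

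The enrolment maximum decides when sites stop enrolling. Sites that follow 4.1 stop about 31 patients short of the accrual target in 14.2, and sites that follow that target exceed the limit in 4.1. Under the lower figure the trial runs without its planned allowance for loss of PFS information. The cost is a longer wait for 133 events or, at a fixed follow-up, somewhat less power.

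**Working it through.** **Inputs (section 14.2).** Medians 25.5 months (Rd) and 44.6 months (BiRd); hazard ratio 1.75; two-sided alpha 0.05; 133 events; accrual 36 months or about 9 patients/month; 12 months of further follow-up; 10% dropout. Allocation is 1:1 (section 4.1).

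**Reproducing the plan's figures.**

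- Events for 90% power (Schoenfeld): 4 × (1.960 + 1.282)² / (ln 1.75)² = 134.2, so 135 against 133 stated. Power at 133 events: Φ(√(133/4) × ln 1.75 − 1.96) = 89.7%.
- With λ = ln 2/median, accrual A = 36 and follow-up F = 12, the event probability is 1 − (e^(−λF) − e^(−λ(A+F)))/(λA). This gives 0.540 for Rd and 0.364 for BiRd. Expected events with 306 and no dropout: 153 × (0.540 + 0.364) = 138.3, or 90.8% power by the formula above. An exponential test at 153 per arm gives 89.6-89.8%.
- Dropout: 306 × 1.10 = 336.6, so 337. Dividing instead, 306/0.90 = 340. The 3-patient difference does not affect the point.

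So 306 is the no-dropout size and 337 is that size with the allowance added.

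**Accrual time.** 9 × 36 = 324, which lies between the two figures and settles nothing. At 9/month, 306 patients take 34.0 months and 337 take 37.4.

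**Effect of the ceiling.** The plan does not define its 10% dropout rate, so three readings are assumed:

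1. 10% of patients contribute nothing.
2. Gradual loss at 0.00495/month, which gives 10% observed dropouts by month 48 with 36 months of accrual.
3. Gradual loss at −ln(0.9)/48 = 0.0022/month, a 10% cumulative loss by month 48.

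For readings 2 and 3, with dropout hazard δ and t = λ + δ, the event probability is (λ/t) × [1 − (e^(−tF) − e^(−t(A+F)))/(tA)]. Power is Φ(√(D/4) × ln 1.75 − 1.96) for D events. Results are in the order of readings 1 / 2 / 3.

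| | 306, 36-month accrual | 337, 36-month accrual | 306 at 9/month | 337 at 9/month |
|---|---|---|---|---|
| Events 12 months after accrual ends | 124.5 / 129.1 / 134.1 | 137.1 / 142.2 / 147.7 | 121.8 / 126.6 / 131.3 | 139.2 / 144.2 / 149.9 |
| Power then (%) | 87.7 / 88.9 / 90.0 | 90.6 / 91.6 / 92.5 | 87.0 / 88.3 / 89.4 | 91.0 / 91.9 / 92.9 |
| Month of 133rd event, from first enrolment | 50.8 / 49.3 / 47.7 | 46.8 / 45.3 / 44.1 | 49.7 / 48.2 / 46.5 | 47.6 / 46.1 / 44.9 |

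The delay in the 133rd event is 3.6-4.0 months if both sizes accrue over 36 months, and 1.6-2.1 months at 9/month. The first comparison implies 306/36 = 8.5 against 337/36 = 9.4 patients/month. A ceiling stops enrolment sooner and does not slow it, so the 9/month comparison is closer to what 4.1 would do.

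At a fixed month 48 and 9/month, 306 patients give 127.9 / 132.5 / 137.8 events and 337 give 134.3 / 139.4 / 144.7. That is 6-7 events, or 1.3-1.4 power points.

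**The case against.** The strongest case against is that little is lost. The plan counts events: "A futility analysis will be conducted after 50% of the total PFS events required for final analysis has occurred". If the final analysis waits for the 133rd event, power is 89.7% with either enrolment figure, and the ceiling costs only time. The no-dropout calculation also has some slack (138 expected events against 133 required), and under reading 3 with 36 months of accrual, 306 patients still reach 134 events and 90.0% power. This stands, and it limits the size of the point.

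A second argument is that 306 could be the evaluable number and 337 the enrolled number. The text does not allow this: 4.1 applies 306 to patients enrolled, and the first sentence of 14.2 applies it to patients accrued.

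A third is that dropouts still contribute, since 10.4 says: "All attempts will be made to follow patients until progression or death". This helps only in part. Table A in 14.3, the primary PFS analysis, has a row "Treatment discontinuation for toxicity or other reason" that censors at the last assessment. Read literally, progression seen later under 10.4 may not count. Follow-up under 10.4 therefore cannot be relied on to replace the allowance.

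A reader might infer more than the documents support:

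- *That the trial is underpowered.* Power stays near 90% at 133 events, and is about 87-90% at a fixed 12 months.
- *That the ceiling costs about four months.* That holds only if both sizes accrue over 36 months.
- *That 4.2 is a further contradiction.* Its 10-15 patients/month fills 306 in 30.6 to 20.4 months and 337 in 33.7 to 22.5 months. This fits its two to three years if completion means accrual. Its rate differs from the 9/month in 14.2, but that is minor wording.

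**Conclusion.** The contradiction is certain. The ceiling in 4.1, the opening sentence of 14.2 and the closing accrual figure of 14.2 cannot all be followed, and the enrolment total is wrong in at least one place.

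The consequence is modest and depends on when the final analysis is taken, which 14.2 implies through its required events but does not state outright.

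- At 133 events: power near 90% either way, with a delay of about 1.6-2.1 months at 9/month (3.6-4.0 months if both sizes take 36 months).
- At 12 months after accrual ends: about 87-90% power with 306, against about 91-93% with 337.

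These ranges rest on exponential PFS at the planned medians, uniform accrual, three assumed readings of 10% dropout and the Schoenfeld approximation. For reading 1 with 36 months of accrual, the exponential-test forms run about a point lower: 86.3-86.5% with 306 and 89.3-89.5% with 337. The size of the effect does not call the design into question, but the figures should be reconciled.

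**What to change.** Use one enrolment figure in 4.1 and in both places in 14.2. Changing 4.1 alone would leave 14.2 in conflict with itself. There are two ways to do it.

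- **(a)** Change the ceiling in 4.1 to the approximately 337 already planned. Reword the first sentence of 14.2 so that 306 is the number required before the dropout allowance, and give an accrual period that matches (337/9 = about 37.4 months). Cost: about 31 more patients than 4.1 now allows, all already planned in 14.2.
- **(b)** Keep 306 throughout and delete the 337 sentence. The sponsor then recomputes and restates power or follow-up with 10% dropout at the stated accrual rate, and says how the 10% is defined. The ranges above should not be copied in, because they depend on assumed dropout readings. Cost: slightly lower stated power at a fixed 12 months, or a few months more follow-up.

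Optionally, use one accrual rate in 4.2 and 14.2 and say whether the completion time in 4.2 refers to accrual. Either option is an edit of a few sentences.
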